5.0 RANDOMIZATION

After all applicable screening assessments have been performed, participants who have met all inclusion criteria and none of the exclusion criteria will be centrally, randomly allocated to one of the two groups in each sub-study. Randomization will be done using computer generated randomization numbers. Treatment **should start within 3 working days after randomization.** Once the order for study drug arrives at the

The PATCH Trial

pharmacy and the participant is randomized only the pharmacist is aware of the assignment of HCQ versus placebo in the double blind sub-studies (1 and 3).

Blinding: Sub-Study 1 and 3 will have a double-blind placebo controlled design.

Unblinding: Sub-Study1: If a participant progresses with symptoms of COVID-19 based on the assessment scale outlined below an appropriately delegated and credentialed study team member will review the case with a clinical investigator who will sign off on the need to un-blind the participant. If the participant was on placebo and continues to have symptoms, then he/she will be allowed to crossover to the HCQ dosing. The EM van will deliver the HCQ to the participant. If the patient was on HCQ then HCQ will be stopped and the patient will be asked to seek the advice of their primary care doctor or go to the emergency room if symptoms are becoming more worrisome. Participants who have progressive symptoms and are subsequently hospitalized due to COVID-19 will be unblinded but not be crossed over to receive HCQ at the time of unblinding.

Sub-Study 3: If the participant at any time has worsening symptoms consistent with new onset of COVID-19 disease a COVID-19 PCR test is performed. Antibody tests alone will not be used to make decisions for this study. If the PCR test is positive for SARS-CoV-2 an appropriately delegated and credentialed study team member will contact IDS and the pharmacist will indicate which arm the participant was assigned. If the participant was assigned to placebo and wishes to cross over to HCQ, IDS will provide HCQ at the same dose as the Sub-Study 3 HCQ arm and IDS will ship the HCQ to the participant. If the participant was assigned to HCQ then the participant will be advised to seek the advice of their personal physician or go to the emergency room if symptoms are becoming more worrisome.

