3. Live attenuated vaccines during the study
4. Herbal and natural remedies must be avoided

7.4 Duration of Protocol Treatment and Follow-up.

Sub-Study 1 duration of treatment is up to 2 weeks or at the time of release from quarantine. HCQ will be stopped in all patients at the time of release from quarantine

Sub-Study 3 duration of treatment is 2 months with assay to assess SARS CoV2 every 2 weeks.

7.5 Crossover from Control to HCQ arm. For Sub-Study 1 all participants are un-blinded upon symptom progression (see response assessment below) after at least 7 days of treatment or upon hospitalization if this occurs prior to 7 days of treatment. If the participant was assigned to placebo, he/she has the option to crossover to receive HCQ 400 mg po bid for up to 2 weeks or until criteria for release from quarantine are met (See 1.0 primary endpoint). During these 2 weeks of HCQ treatment, the patient will continue to complete the daily diary. An appropriately delegated study team member will call the patient daily to assess worsening symptoms and AEs. Patients who are not improving will be sent to the hospital for further care. Participants who have progressive symptoms and are subsequently hospitalized as related to COVID-19 will not be crossed over to receive HCQ at the time of unblinding.

In sub-study 3 participants who have worsening symptoms as defined as fever, significantly worsening cough, shortness of breath or hypoxia but do not require hospitalization and tests positive for SARS-CoV2 virus are allowed to cross over to receive HCQ, or treated with an alternative therapy per physician's choice. Once the positive test returns, the CRC will email IDS to initiate unblinding IDS will inform the CRC and clinical investigator if the patient was on placebo. The clinical investigator will contact the subject and inform them that if they were on placebo they would have the option of being treated with HCQ 600 mg qd. If the patient agrees, the clinical investigator will place the order in EPIC for HCQ 600 mg qd through IDS. Drug will be delivered to the patient's home. During these 2 weeks of HCQ 600 mg po qd treatment, clinical investigators will call the patient every 1-3 days depending on the severity of symptoms to assess worsening symptoms and AEs. Patients who are not improving will be sent to the hospital for further care.

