Asymptomatic PCR+ at baseline: Given the 20% prevalence of asymptomatic coronavirus infection, we will need to screen 250 subjects to accrue the target enrollment of 200 to address the primary endpoint. If the PCR test returns positive while the health care worker is enrolled on the study, the participant will be notified and offered to be removed from the study or to continue with the study medication. Baseline PCR+ subjects who decide to withdraw from the study will be asked to go to occupational health and seek the care of their primary physician. Their study medication will remain blinded and the subject will be asked not to take any additional study medication. For baseline PCR+ subjects who decide to continue on study, they will be asked to keep the daily pill diary. If these subjects are asymptomatic after one week of study medication, they will be asked to return to undergo an on treatment nasopharyngeal swab. If the subject develops symptoms on study medication after 7 days of treatment, the subject will be unblinded. If the subject was assigned to placebo, they will have the option to crossover and get treatment with HCQ 600 mg qd for up to 7 days. Weekly phone calls per the sub-study 3 schedule will continue during this time. AEs will be reported as planned for the study. Baseline PCR+ subjects will be replaced in the prevention study related to the primary objective of sub-study 3 and will not count towards the target accrual or interim analysis. Baseline PCR negative subjects who screen positive at the one month or two-month mark will be considered COVID-19 positive as it relates to the primary endpoint.

Asymptomatic PCR+ at one month: These subjects will count towards the primary endpoint of sub-study 3 as an infection event. Accordingly, they will be unblinded and if on placebo they will be allowed to crossover to HCQ 600 mg qd for 2 weeks. If the subject is assigned to HCQ and turns PCR positive while asymptomatic, the subject will be stopped from study drug and referred to occupational health for standard of care management of health care worker infection. Weekly phone calls will continue. If the subject remains asymptomatic after one month, he/she will return for the one-month swab.

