Clinical Symptom monitoring: Appropriately delegated and credentialed study team members (as example: CRC) will screen for symptoms 1X per week and if present will document the likely treatment related AEs. Follow up with an appropriately delegated and credentialed physician investigator will be undertaken for assessment and grading of events. Participants will be asked if there have been changes in vision such as distortions of blurred vision. Patients who develop COVID-19 symptoms will be instructed to go to occupational health for nasopharyngeal swab. The rate of conversion to PCR positive in each arm at the 2-month mark will be used to assess the primary endpoint.

Electrocardiogram Recordings: An electrocardiogram (12 lead or 6 lead) will be recorded at baseline prior to the initiation of the study drug. Those participants with an ECG in the last 6 months and no QTc prolonging medications do not need a repeat baseline ECG. One month after starting the study drug a repeat ECG will be performed to confirm excessive QTc prolongation has not occurred. If the QTc has prolonged to >500ms dose reduction as described below will be attempted to achieve a QTc of <500ms. Due to the long half-life of HCQ, study medication can be started before the baseline ECG is read.

Pill diary: Electronic pill diary will be turned in by the participant at the end of the study.

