10.3 Off treatment/Off Study

Each participant has the right to withdraw from the study at any time without prejudice. The investigator may discontinue any person's participation for any reason, including adverse event or failure to comply with the protocol. Should a participant withdraw from the study, the reason(s) must be stated on the case report form, and a final evaluation of the participant should be performed. Reasons for withdrawal include the following:

Progression of Disease: Remove participant from protocol therapy at the time progressive disease is documented. Progression of disease is left to the discretion of the treating physician/ sub-Investigator; however, the following guidelines are provided to help decision making for discontinuing study drug:

Sub-study 1: Progression of disease can be confirmed if there is increase in COVID-19 symptom score for 2 days in a row and is three points higher than baseline. Once criteria for release from quarantine is met in SS1 the patient is off study. Once the person is hospitalized for COVID-19 in sub-study 1 the subject is off study. Participants who have progressive symptoms and are subsequently hospitalized as related to COVID-19 will not be crossed over to receive HCQ at the time of unblinding.

Sub-study 3: Development of new symptomology consistent with COVID-19: e.g. fever, cough, shortness of breath and SARS-COV2 test positivity would lead to unblinding. If on placebo the subject can crossover to HCQ for treatment and stay on study for 14 days or release from quarantine. If the subject was on HCQ the subject is off study and will be instructed to seek medical attention through their primary care physician

Extraordinary Medical Circumstance: If at any time the treating physician feels constraints of this protocol are detrimental to the participant's health remove the participant from protocol therapy.

Participant's refusal to continue treatment: In this event, document the reason(s) for withdrawal.

Failure to comply with protocol (as judged by the investigator such as compliance below 80%, failure to maintain appointments, etc.).

Withdrawal from treatment per patient choice: Patients may withdraw from study treatment at any point in the study for any reason. These subjects are allowed to withdraw from treatment but continue to participate with any of the other study procedures for the intended 2 month period.

Delay in treatment > 7 days due to toxicity

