In addition, at our second interim analysis for SS3, we will evaluate the conditional power based on our original assumptions. The actual effect size for this study is completely unknown. If the effect size is smaller than we anticipated but still promising, and our conditional power falls between 0.5 and 0.8, we will consider formally adjusting the sample size in SS3 to achieve a conditional power of 0.8 based on an updated understanding of the effect size (29).

Z-Value Boundaries			
	Boundaries		Information
Stage	Efficacy	Futility	Proportion
1	2.9473	-1.2318	0.2500
2	2.5825	-0.2676	0.5000
3	1.6664	1.6664	1.0000

P-Value Boundaries			
	Boundaries		Information
Stage	Efficacy	Futility	Proportion
1	0.00160	0.89099	0.2500
2	0.00491	0.60550	0.5000
3	0.04782	0.04782	1.0000

12.2 Analysis of Secondary Endpoints.

Secondary outcomes will at least be analyzed as summary statistics, with group means, odds-ratios, and 95% CIs. We may conduct exploratory analyses using regression methods appropriate for each type of measure.

Sub-Study 1: Rate of secondary infection of housemates is a binomial count by household. We will summarize the proportion or rate by group, with 95% CI. With sufficient data, we will explore subgroups, patient, and secondary patient characteristics using logistic regression. Rate of hospitalization is a binary measure. We will summarize rates by group, and estimate the odds-ratio for treatment. Adverse event rates will be summarized as a count by subject, and mean count by group, and we will estimate a rate-ratio for treatment.

Sub-Study 3: For hospital employees, Adverse event rates will be summarized as a count by subject, and mean count by group, and we will estimate a rate-ratio for treatment.

REFERENCES

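### In sub-study 3, adverse-event follow-up after symptomatic infection differs by arm and crossover time has no analysis rule, so the rate ratio can be biased, most likely toward HCQ looking safer

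*Protocol*

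**What the plan says.** **Symptomatic, PCR positive.** For the HCQ arm, Protocol 10.3 states: "If the subject was on HCQ the subject is off study and will be instructed to seek medical attention through their primary care physician". For the placebo arm: "If on placebo the subject can crossover to HCQ for treatment and stay on study for 14 days or release from quarantine". Section 7.5 adds that during the two weeks of crossover HCQ "clinical investigators will call the patient every 1-3 days depending on the severity of symptoms to assess worsening symptoms and AEs". Crossover is a choice; section 5.0 begins the rule with "If the participant was assigned to placebo and wishes to cross over to HCQ".

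**Asymptomatic, PCR positive at one month.** Protocol 8.4.2 unblinds these participants. Those on placebo may take HCQ for two weeks. For those on HCQ, "the subject will be stopped from study drug and referred to occupational health". It then says: "Weekly phone calls will continue".

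**Routine contact.** In 8.4.2 the study team "will screen for symptoms 1X per week and if present will document the likely treatment related AEs". The SAP (Secondary Objectives) takes treatment-related adverse events from weekly calls to all subjects.

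**Reporting window.** Protocol 11.0 and the SAP both run it from the first to the last administration of study treatment.

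**Analysis.** Protocol 12.2, for sub-study 3: "Adverse event rates will be summarized as a count by subject, and mean count by group, and we will estimate a rate-ratio for treatment". The SAP's safety set is everyone randomized who took one dose, and only observed values are used. Neither document states censoring at unblinding, an as-treated rule or a person-time offset.

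**The concern.** After a symptomatic infection, an HCQ participant leaves and the reporting window closes with the last dose. A placebo participant who crosses over goes on contributing for up to two weeks, now taking HCQ, unblinded, ill and called more often. On the natural reading of the group comparison, those events belong to the placebo mean. Events on the active drug would then raise the comparator's rate and pull the HCQ/placebo ratio down.

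The rate of treatment-related adverse events is the only secondary objective listed for sub-study 3, although the SAP's amendment table also calls QTc change a secondary endpoint. For a prophylactic given to healthy workers, an understated safety ratio matters.

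**Working it through.** Neither document gives an adverse-event rate, ratio or power, so there is no figure of the plan to reproduce. The check is an expected-count model.

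**Inputs from the documents.** 100 per arm; 8 weeks; infection 10% on placebo and 1% on HCQ (planning rates), with 3.8% and 58% as the cited range; crossover of 2 weeks; calls every 1-3 days in crossover against weekly otherwise.

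**Assumptions.** True ratio r = 1.5. Infection at week T = 4. All infections follow the symptomatic path. All infected placebo participants cross over and leave after 14 days. Yield multiplier k for the extra calls: k = 1 if they find nothing more. If yield is proportional to calls, k = (14/3)/2 = 2.33 for calls every 3 days and k = 14/2 = 7 for daily calls, taken as an upper bound.

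**Formulas** (expected events per 100 participants, in units of the weekly placebo rate):

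- HCQ: r × [uninfected × 8 + infected × T]
- Placebo: uninfected × 8 + infected × (T + 2 × k × r)

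**Planning rates, T = 4.** HCQ: 1.5 × (99 × 8 + 1 × 4) = 1.5 × 796 = 1194. Placebo: 90 × 8 + 10 × (4 + 3k) = 720 + 10 × (4 + 3k).

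- k = 1: 1194/790 = 1.51
- k = 2.33: 1194/830 = 1.44
- k = 7: 1194/970 = 1.23

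**Other cases, true ratio still 1.5:**

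| Infected, placebo v HCQ | T | k = 1 | k = 2.33 | k = 7 |
|---|---|---|---|---|
| 10% v 1% | 4 | 1.51 | 1.44 | 1.23 |
| 10% v 1% | 8 | 1.45 | 1.38 | 1.19 |
| 10% v 10% | 4 | 1.44 | 1.37 | 1.18 |
| 3.8% v 3.8% | 4 | 1.48 | 1.45 | 1.36 |
| 58% v 58% | 4 | 1.15 | 0.87 | 0.48 |

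The first cell lies just above 1.5 because ten placebo participants lose weeks 7 and 8 while only one HCQ participant is lost at week 4. The T = 8 row supposes that crossover runs past week 8, which the two-month limit in 10.3 may prevent.

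**Scale.** Crossover time at the planning rate is at most 10 × 14 = 140 person-days of 100 × 56 = 5,600, or 2.5% of the placebo arm. The size therefore depends on how much the extra calls raise yield.

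**Proposed analysis, 10% v 1%, T = 4.** Cutting at infection leaves 90 × 8 + 10 × 4 = 760 placebo and 796 HCQ person-weeks. With the offset, (1194/796)/(760/760) = 1.50. Cutting without the offset gives 1194/760 = 1.57. An offset without cutting gives 1.48, 1.41 and 1.21 for the three values of k. Both parts are needed.

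**The case against.** Several points count against a stronger reading, and most of them stand.

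- **Contradiction.** A reader might infer that 10.3 and 8.4.2 contradict each other on infected HCQ participants. They cover different groups: 10.3 those with symptoms and a positive test, 8.4.2 asymptomatic positives at one month. It is therefore also wrong that every infected HCQ participant loses contact. What remains open is how the continued calls fit a reporting window that closes at the last dose.
- **Automatic crossover.** Crossover is optional, and 7.5 also allows another therapy. The calls every 1-3 days belong to the symptomatic path. Sending all infected placebo participants down that path overstates the effect.
- **Events counted.** The SAP names weekly calls as the source and does not say whether events from the extra calls enter the endpoint. Counting them as placebo events is the default reading, not a stated rule.
- **Treatment-related events only.** Section 11.2.2 makes an event unrelated when intercurrent illness explains it. Against that, 11.2.1 supports relatedness when an event fits the drug's known pattern, and crossover is unblinded. Serious events are collected from consent in any case.
- **Direction.** At the planning rates with infection at week 4 and no added yield, the ratio is 1.51, slightly against HCQ.

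One point works the other way. Protocol 8.4.2 expects 20% asymptomatic infection at baseline. Those who continue are in the safety set and, if on placebo, may cross over on developing symptoms after 7 days. The model leaves them out.

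**Conclusion.** The point holds in a limited form. For symptomatic PCR-positive participants the follow-up differs by arm, HCQ exposure can be counted as placebo, and no analysis rule deals with either. The ratio can be biased, and most likely makes HCQ look safer: every case run with k of 2.33 or more goes that way. With k = 1 the direction depends on timing, infection rates and the true ratio.

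At the planning rates with infection at week 4, a true 1.5 would appear as about 1.51, 1.44 or 1.23. The last assumes yield in proportion to daily calls. These figures rest on the assumed timing, full crossover uptake, true ratio and yield.

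A reader might infer that the ratio would fall to 1 or below. At a true ratio of 1.5 this does not follow at the planning rates. With a placebo mean of 0.5 to 1.0 events over 8 weeks, two weeks on HCQ yields 0.5 × 1.5 × 2/8 = 0.19 to 1.0 × 1.5 × 2/8 = 0.38 events before any extra ascertainment. In the cases above, the ratio drops below 1 only at 58% infection with raised yield.

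**What to change.** In the SAP, for the randomized comparison, count adverse events in both arms only up to the positive PCR or unblinding, with person-time as offset. For participants already positive at baseline who continue, unblinding is the usable cut. Tabulate events during crossover HCQ separately, as on-HCQ events, and say whether events from the 1-3 day calls are included there.

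In the protocol, reconcile 7.5, 8.4.2, 10.3 and the reporting window in 11.0, so that it is clear which adverse events are recorded after infection in each arm and for how long.

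The cost is wording; the dates and calls are already planned. The event window becomes slightly shorter: 760 of 800 placebo and 796 of 800 HCQ person-weeks remain in the planning scenario. The ratio then describes event rates before infection or unblinding. The model's exact recovery of 1.50 assumes a constant event rate over time within each arm.

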8.2 Dose Delays

Major Events are grade 3 and 4 hematologic and non-hematologic toxicities that are not treatment -related. Treatment should be delayed for major events if HCQ may further complicate the non-treatment related event. If a major event requires a delay of treatment, treatment must be delayed until toxicity is resolved (\leq Grade 2 or \leq Baseline). For treatment-related toxicities and major events, if toxicity is not resolved in \leq 14 days, patient will be taken off treatment unless there is an exception granted by the medical monitor.

8.3 Ocular toxicity. The only toxicity that requires discontinuation of HCQ is retinopathy. Published literature indicates HCQ retinopathy is idiosyncratic and is uncommon in patients receiving HCQ for less than a few years. Our ongoing study of dabrafenib, trametinib, and HCQ (BAMM; NCTNCT02257424) found no clinically meaningful ocular toxicity in 10 patients studied extensively with serial ocular exams (25). Although HCQ retinotoxicity can occur at shorter than expected intervals with the use of high dose (>5 mg/Kg/day of real body weight) treatment protocols, the cumulative doses required to elicit a retinopathy were only reached after about a year of treatment (26). Thus, we do not anticipate cumulative doses in this trial will reach retinotoxic levels (>200 grams) and have, therefore, not included mandatory ocular exams in this protocol. However, participant will be advised to report with any visual changes at which point a comprehensive ophthalmic exam will take place to decide whether HCQ should be permanently discontinued. As a precaution, patients with renal failure will also be excluded from the trial.

Laboratory monitoring is not recommended for HCQ use in rheumatoid arthritis. The American College of Rheumatology guidelines for the treatment of rheumatoid arthritis recommends no laboratory testing for outpatients that are started on hydroxychloroquine (27). HCQ doses for rheumatoid arthritis range from 400mg daily to 400mg twice a day encompassing the dosing paradigms in Sub-study 1 and sub-study3.

8.3 Safety of HCQ in pregnancy obviates the need for pregnancy monitoring. Numerous case series and a recent large scale epidemiological study demonstrate the safety of HCQ in outpatient pregnant women with systemic lupus erythematosus (28). Therefore we are not requiring pregnancy test prior to starting HCQ in sub-studies 1 and 3. Potential participants that are known to be pregnant are excluded.

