Toxicities that may be attributable to HCQ include: nausea, anorexia, vomiting, constipation, diarrhea, rash, and visual field deficit. If any of these AEs occur at grade < 2, HCQ may be continued and the AE managed with supportive care. For any AE with a grade ≥ 3, HCQ dose will be held until the toxicity resolves to ≤ grade 2, after which HCQ may be restarted at a reduced dose as described in table 5. With particular regard to visual field deficits participants should be cautioned to report any visual symptoms, particularly difficulty seeing entire words or faces, image distortions, intolerance to glare, decreased night vision, or loss of peripheral vision. **These symptoms of retinal toxicity or subclinical evidence of retinal toxicity on eye exam should prompt drug discontinuation and ophthalmologic evaluation at Scheie Eye Institute Urgent care.** The natural course of COVID_19 is not fully understood and additional toxicities attributable to HCQ may emerge when used to treated COVID-19.

8.6 Procedure for handling of potentially contaminated material: For sub-study 1 institutional and CDC guidelines will be followed. Patients and subjects on sub-studies 1 and 3 will be instructed on safe practices for storage of oral fluid and disinfection of outer layers of bags and receptacles. Proper hand washing techniques will be reviewed with subjects. Changes in recommendations from the CDC or the University of Pennsylvania will be immediately implemented.

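### Protocol sections 8.2 and 10.3 set different limits on a toxicity-related treatment delay, and 10.3 does not say whether its limit ends study drug or study participation

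*Protocol*

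**What the plan says.** Protocol 8.2 (Dose Delays) covers both related and unrelated events. It opens "For treatment-related toxicities and major events, if toxicity is not resolved in" and, after a less-than-or-equal sign, continues "14 days, patient will be taken off treatment unless there is an exception granted by the medical monitor". The limit is 14 days, counted to resolution. The consequence is the end of treatment, and the medical monitor can waive it.

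Protocol 10.3 (Off treatment/Off Study) introduces a list with "Reasons for withdrawal include the following". The last reason in that list is "Delay in treatment > 7 days due to toxicity". It carries no exception, does not refer to 8.2, and does not say what ends.

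Protocol 8.5 (Hydroxychloroquine Dose Reduction) adds that for events of grade 3 or above the "HCQ dose will be held until the toxicity resolves to" grade 2 or lower, without a time limit.

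On duration, protocol 7.4 states "Sub-Study 1 duration of treatment is up to 2 weeks or at the time of release from quarantine" and "Sub-Study 3 duration of treatment is 2 months with assay to assess SARS CoV2 every 2 weeks". The SAP gives the Sub-Study 3 course as eight weeks.

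**The concern.** A stopping limit should give one answer for one case. Here the number of days differs, one rule can be waived and the other cannot, and only one of them says what it ends.

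Two things are at stake. The first is consistent conduct: staff could remove a participant on day 8 or allow a restart on day 10, and either action departs from one section. The second is follow-up. Item by item, 10.3 mixes removal from therapy with going off study. The only item that says study procedures may continue is the one on withdrawal from treatment by the participant's own choice. If a toxicity delay is handled as an exit from the study, a Sub-Study 3 participant may miss the remaining 4- or 8-week swab. The SAP imputes nothing and uses observed values only. Holds for toxicity could plausibly be more frequent on hydroxychloroquine than on placebo, in which case the loss would be related to arm.

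There is also a smaller effect on safety data. Protocol 11.0 and the SAP end the adverse event reporting period at the last administration of study treatment. Whether a participant resumes after a hold therefore changes how long new events must be reported. Treatment-related adverse events are the secondary objective of Sub-Study 3.

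**Working it through.** No sample size, power or alpha figure is involved, so the check sets the two rules side by side by length of a toxicity-related delay, *d*.

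| Delay *d* | Section 8.2 | Section 10.3 | Result |
|---|---|---|---|
| up to 7 days | on hold, may resume | no reason for withdrawal | agree |
| more than 7, up to 14 days | on hold, may resume | reason for withdrawal | conflict |
| more than 14 days, no exception | off treatment | reason for withdrawal | agree that drug stops; participation unclear |
| more than 14 days, exception granted | may stay in treatment | reason for withdrawal, no exception | conflict |

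**The clocks.** Section 8.2 counts days until the toxicity resolves; 10.3 counts days of delay. Where a major event (a grade 3 or 4 toxicity not related to treatment) requires a delay, 8.2 delays treatment until resolution, and 8.5 holds the drug for grade 3 or above until improvement. In those cases the two counts largely coincide. They separate when a grade 2 event is managed by dose reduction without a hold, which 8.5 allows; then there is no delay and 10.3 is not triggered. The table applies to held doses.

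**Scale against the treatment course.**
- Sub-Study 3, 8 weeks = 56 days: 7/56 = 12.5% and 14/56 = 25%.
- Sub-Study 1, at most 14 days: 7/14 = 50% and 14/14 = 100%. The 14-day limit could hardly ever take effect within the course. A hold of 8 days leaves at most 14 − 8 = 6 days of dosing, so the choice of limit has little room to matter there. The practical weight is in Sub-Study 3.

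**Does other text reconcile them?**
- Section 8.5 has no time limit.
- Section 8.3 (Ocular toxicity) says retinopathy is the only toxicity that requires hydroxychloroquine to be discontinued. Read literally, that fits neither limit.
- The original protocol, reproduced in the same supplement, contains the same pair of limits. The conflict is therefore not produced by comparing versions.
- The SAP does not mention either limit.

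**Effect on the primary analysis.** Protocol 10.1 makes a participant evaluable after one dose, given the required PCR status (negative for Sub-Study 3). Leaving study drug does not change that. The SAP's own definition of the primary-outcome set breaks off mid-sentence in the text available, so it is not used here in either direction.

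**The case against.** The strongest reply is that the two sections can be read together. The general wording of 10.3 is partly permissive: the investigator may discontinue a person, and the list gives reasons rather than commands. On that reading, more than 7 days of delay permits withdrawal, and more than 14 days requires the end of treatment unless excepted. The reading is coherent, but the protocol does not state it. The 10.3 item has no discretion of its own, and neither section refers to the other.

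Three stronger readings are tempting, and the documents do not support them.

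- *A reader might infer that 8.2 keeps the participant taking drug while 10.3 withdraws them.* During a delay the dose is on hold under both rules. The difference is whether the participant may still resume.
- *A reader might infer that 8.2 ends treatment while 10.3 ends participation.* The lead-in to 10.3 does speak of withdrawal from the study. But its heading covers both, and several items concern therapy only. The toxicity item is silent, so what can be shown is ambiguity.
- *A reader might infer that participants are lost from the primary outcome, and more of them on hydroxychloroquine.* Under 10.1, going off drug does not remove anyone. No section gives a rate of such delays in either arm. The nearest figure, in protocol 2.3, is below 10% for grade 3–4 non-hematological toxicity in over 220 cancer patients, most of which the authors would not expect in a healthy population.

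Follow-up off drug is also partly covered. The protocol's summary of Amendment 4 and the SAP's amendment table both say, without limiting it to patient choice, that subjects off study medication can complete study procedures. That shows the intent. The operative sentence in 10.3 still sits under patient choice.

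**Conclusion.** The conflict stands. The current protocol gives two limits for a toxicity-related delay, and they lead to different permitted actions when the delay is more than 7 and up to 14 days, or longer with an exception from the medical monitor. In addition, 10.3 leaves open whether its limit ends drug or participation.

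Its size cannot be put as a number of participants, because the documents do not state how often such delays are expected. The risk to outcome data is conditional: it arises only if the 10.3 item is applied as off study, and it would bias the arm comparison only if the resulting loss differed by arm in a way related to infection risk. That holds could be more common on hydroxychloroquine is an assumption, with no rate behind it here.

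The point warrants correction as a conflicting stopping threshold. It does not show that the primary analysis is invalid, and it gives no basis for preferring either limit.

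**What to change.** 1. Reconcile 8.2 and 10.3 so that a toxicity-related delay has one rule. State which clock it uses (days of delay or days to resolution) and whether the medical monitor's exception applies. The choice of limit is a clinical matter for the sponsor. Check the retinopathy sentence in 8.3 against the result in the same edit.
2. In 10.3, say whether the criterion ends study drug only or also study participation.
3. Extend the continued-procedures wording now under patient choice to discontinuation for toxicity, so that the scheduled Sub-Study 3 swabs and weekly calls continue off drug for the intended two months. This matches what the amendment summaries already describe in general terms.

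The cost is protocol wording and the review of an amendment. Sample size, interim boundaries and the primary analysis do not change. Continued follow-up uses visits and calls that are already scheduled.
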